5.4.1 Use of DataCore/Epic Information for Recruitment Purposes

This study will utilize the institutional electronic medical record, Epic, to identify subjects.

The following elements will be submitted in the recruitment process via DataCore:

- Study personnel will subject a request to NYU Langone Health DataCore via iLab
- Study team members by role who will have access to search results
- Study eligibility criteria that include age, gender, admission diagnosis of acute bronchiolitis
- Data will be discarded 30 days after use and will be discarded by shredding paper documents and any electronic data obtained will be deleted.
- The study team is projected to search DataCore/Epic monthly bi-monthly over the course of the study and queries regarding eligible cases will run bi-month during the course of the study.

5.5 Duration of Study Participation

The duration of study participation will be from beginning of admission to the general inpatient pediatrics unit until the time of discharge from the general inpatient pediatrics unit. No follow up time period is required. This is a single phase pilot study.

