4.2 Study Endpoints**4.2.1 Primary Study Endpoints**

The primary study endpoints will be length of hospital stay expressed in days and the time on supplemental oxygen support expressed in days, and these endpoints will be compared between the control and experimental group.

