5.2 Exclusion Criteria

An individual who meets any of the following criteria will be excluded from participation in this study:

1. Admitted to the pediatric intensive care unit
2. Has an underlying pre-existing condition that may affect the respiratory system (includes bronchopulmonary dysplasia, reactive airways disease, asthma, restrictive lung diseases, other chronic lung diseases, etc.)
3. Has other comorbid conditions upon admission that may affect the respiratory system (includes pneumonia or other bacterial or fungal lung infections, acute exacerbation of reactive airways disease, acute exacerbation of asthma, pulmonary edema, pleural effusion, etc.)
4. Has an absolute contraindication to nebulized 3% hypertonic saline, for example, a history of an allergic or anaphylactic reaction
5. Is receiving other respiratory treatments such as bronchodilator treatments (i.e. albuterol or levalbuterol)
6. Is receiving other adjuvant therapy such as antibiotics, antivirals, glucocorticoids, corticosteroids, or diuretics

A potential study subject in the control arm via retrospective chart review who meets any of the following criteria will be excluded from this study:

1. Admitted to the pediatric intensive care unit
2. Has an underlying pre-existing condition that may affect the respiratory system (includes bronchopulmonary dysplasia, reactive airways disease, asthma, restrictive lung diseases, other chronic lung diseases, etc.)
3. Has other comorbid conditions upon admission that may affect the respiratory system (includes pneumonia or other bacterial or fungal lung infections, acute exacerbation of reactive airways disease, acute exacerbation of asthma, pulmonary edema, pleural effusion, etc.)
4. Has an absolute contraindication to nebulized 3% hypertonic saline, for example, a history of an allergic or anaphylactic reaction
5. Is receiving other respiratory treatments such as bronchodilator treatments (i.e. albuterol or levalbuterol)
6. Is receiving other adjuvant therapy such as antibiotics, antivirals, glucocorticoids, corticosteroids, or diuretics

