5.7 Participant Withdrawal or Termination

5.7.1 Reasons for Withdrawal or Termination

Participants are free to withdraw from participation in the study at any time upon request. An investigator may terminate participation in the study if:

- Any clinical adverse event (AE), laboratory abnormality, or other medical condition or situation occurs such that continued participation in the study would not be in the best interest of the participant

- The participant meets an exclusion criterion (either newly developed or not previously recognized) that precludes further study participation

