5.7.2 Handling of Participant Withdrawals or Termination

There is no follow up period required in this study after patients are discharged from the general inpatient pediatrics unit and participation in the study has been completed. Participants may choose to withdraw from the study at any time and no information prior to or after withdrawal will be collected from this participant to be utilized in this clinical study. Upon participant withdrawal or termination, every effort will be made to undertake protocol-specific safety follow up procedures to capture adverse events, serious adverse events, and unanticipated problems. Given the safe profile of the medication (nebulized 3% hypertonic saline) and device (chest percussion cup) used, there is no anticipated risk of adverse events or serious adverse events.

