7.3.4 Final Study Visit

Final Study Visit (Day of hospital discharge)

- Record adverse events as reported by participant or observed by investigator.
- Record vital signs to include respiratory rate, heart rate, and oxygen saturation.
- Record time of supplemental oxygen support order discontinuation.
- Record subjective responses from providers and caretakers on participants' clinical response to treatment.
- Record participant's adherence to treatment regimen.

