8.3 Time Period and Frequency for Event Assessment and Follow-Up

The occurrence of an AE or SAE may come to the attention of study personnel during study visits and interviews of a study participant presenting for medical care, or upon review by a study monitor. All AEs including local and systemic reactions not meeting the criteria for SAEs will be captured on the appropriate RF. Information to be collected includes event description, time of onset, clinician's assessment of severity, relationship to study product (assessed only by those with the training and authority to make a diagnosis), and time of resolution/stabilization of the event. All AEs occurring while on study must be documented appropriately regardless of relationship. All AEs will be followed to adequate resolution.

Any medical condition that is present at the time that the participant is screened will be considered as baseline and not reported as an AE. However, if the study participant's condition deteriorates at any time during the study, it will be recorded as an AE. UPs will be recorded in the data collection system throughout the study.

Changes in the severity of an AE will be documented to allow an assessment of the duration of the event at each level of severity to be performed. AEs characterized as intermittent require documentation of onset and duration of each episode.

The PI will record all reportable events with start dates occurring any time after informed consent is obtained until 7 (for non-serious AEs) or 30 days (for SAEs) after the last day of study participation. At each study visit, the investigator will inquire about the occurrence of AE/SAEs since the last visit. Events will be followed for outcome information until resolution or stabilization.

All unresolved adverse events should be followed by the investigator until the events are resolved, the subject is lost to follow-up, or the adverse event is otherwise explained. At the last scheduled visit, the investigator should instruct each subject to report any subsequent event(s) that the subject, or the subject's personal physician, believes might reasonably be related to participation in this study. The investigator should notify the study sponsor of any death or adverse event occurring at any time after a subject has discontinued or terminated study participation that may reasonably be related to this study.

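### How a child moved to intensive care counts towards hospital stay and oxygen time is undefined, and the plan allows treated children who deteriorate to be dropped or cut off after treatment began.

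*Combined protocol and SAP*

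**What the plan says.** All references are to the combined protocol and SAP.

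- **Endpoints.** Section 4.2.1: "The primary study endpoints will be length of hospital stay expressed in days and the time on supplemental oxygen support expressed in days". It gives no start or stop time for either.
- **End of participation.** Section 5.5 runs it "until the time of discharge from the general inpatient pediatrics unit. No follow up time period is required", and the synopsis gives the same end. Section 5.7.2 adds: "There is no follow up period required in this study after patients are discharged from the general inpatient pediatrics unit".
- **Final visit.** Section 7.3.4 places it on the day of hospital discharge and records there when the oxygen order was discontinued.
- **Intensive care.** Section 5.2 lists "Admitted to the pediatric intensive care unit" as an exclusion, identically for both arms. It does not say whether this means at admission, at enrolment or at any time in the stay.
- **Termination.** Under section 5.7.1 the investigator may end participation if "The participant meets an exclusion criterion (either newly developed or not previously recognized) that precludes further study participation".
- **Analysis after termination.** Section 10.4.5 removes from the study anyone who withdraws or is terminated early, for any reason.
- **Early termination visit.** Section 7.3.5 lists adverse events, vital signs, current oxygen settings, survey responses and adherence. It lists neither hospital discharge time nor oxygen stop time.
- **Safety window.** Section 8.3 records events "until 7 (for non-serious AEs) or 30 days (for SAEs) after the last day of study participation".

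**The concern.** For a child who goes home from the general unit, unit discharge and hospital discharge coincide. For a child who worsens and moves to intensive care they do not, and that is a child whose stay and oxygen time are likely to be long. If such children are removed, or counted only up to transfer, an outcome that arose after treatment began decides who contributes to the primary analysis and with what value. Both primary endpoints are affected. The study is open and non-randomized, with a historical control group, so nothing else in the design would offset a difference between the groups in how these children are handled.

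**Working it through.** **Passages side by side.** A treated child transferred on day 2 could be handled in three ways:

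1. *Dropped.* Sections 5.2, 5.7.1 and 10.4.5 together: the exclusion is newly met, participation may be ended, and the child is left out. This route has the most textual support.
2. *Cut off at transfer.* Sections 5.5 and 5.7.2, if leaving the unit is read as discharge from it. This is possible but nowhere stated.
3. *Followed to hospital discharge.* Sections 4.2.1 and 7.3.4.

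Controls are found by retrospective chart review (sections 4.1 and 5.1), with the whole course visible, whereas treated children are judged at enrolment (sections 7.3.1 and 7.3.2). The same unanchored exclusion can therefore work differently in the two groups.

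**The plan's own figure.** Section 10.5: mean 6.5 days, SD 3.5, 20% decrease, type I error 0.05, power 0.80.

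- Target difference = 0.20 × 6.5 = 1.3 days.
- n per group = 2 × (1.960 + 0.842)² × 3.5² / 1.3² = 113.8, so 114 per group and 228 in total. The stated size reproduces (two-sided, normal approximation; power 0.801).

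**Illustration.** The documents give no transfer rate and no stay for transferred children, so these inputs are assumptions: share transferred p = 5%, their true stay 10 days, ward days before transfer 2, true mean 6.5 days in both arms.

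- Dropped: mean of the rest = (6.5 − 0.05 × 10) / 0.95 = 6.32, a fall of 0.18 days.
- Cut off: 0.05 × (10 − 2) = 0.40 days.

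| Treated | Controls | Net shift towards treatment |
|---|---|---|
| cut off | dropped | 0.40 − 0.18 = 0.22 days (17% of 1.3) |
| dropped | dropped, same p | about 0 |
| followed to hospital discharge | dropped | −0.18 days (against treatment) |

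Identical handling is not enough if transfer rates differ. With 10% of treated children transferred, dropping them lowers that mean by 6.5 − (6.5 − 0.10 × 10) / 0.90 = 0.39 days. Against 5% of controls dropped, the net is 0.39 − 0.18 = about 0.21 days towards treatment.

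**Range for one arm.** With p from 2% to 15% and a true stay of 8 to 12 days, dropping lowers the mean by 0.03 to 0.97 days (2% to 75% of 1.3). Cutting off at 1 to 2 days lowers it by 0.12 to 1.65 days (9% to 127%).

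**Error rate if only one arm were affected.** SE = 3.5 × √(2/114) = 0.464. A shift of 0.18 days raises the two-sided 5% error rate to about 6.7%, and 0.40 days raises it to about 13.9%.

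**The case against.** A reader might infer that data capture stops at transfer in the experimental arm alone, so that treatment failure is scored as a favourable short stay. The documents do not support that:

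- Section 5.5 defines participation, not the stop time of the endpoint. Section 4.2.1 names hospital stay and section 7.3.4 puts the last visit at hospital discharge. The correct description is a conflict to be reconciled.
- Section 5.7.1 says the investigator may terminate, so removal is permitted, not required. On that route the child has no value at all rather than a short one.
- The exclusion in section 5.2 is the same for both arms. If it covers later transfers in both, and transfer rates match, the between-group shift is about zero.

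A reader might also multiply 5–15% transferred by 3–6 days cut off, obtain 0.15–0.90 days (12–69% of 1.3) and treat that as the between-group bias. Both inputs are assumed, and the product leaves the control mean untouched even where controls who went to intensive care are excluded, which lowers that mean too.

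Nor would deterioration vanish from the safety record. Section 8.3 records it as an adverse event, section 8.1.2 makes an event serious if it prolongs hospital stay, and section 10.4.4 lists events leading to discontinuation. However, the 7- and 30-day windows collect events rather than stay or oxygen time, and they start from the last day of participation, which is the date in dispute.

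What stands is that no transfer rule exists, and that the plan as written permits removal on a post-treatment outcome.

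**Conclusion.** The concern holds as an undefined endpoint rule combined with permitted post-treatment removal. It affects both primary endpoints, though only stay is quantified here. Cutting off lowers the experimental mean relative to the full stay. Dropping lowers it provided transferred children stay longer than the rest, which is assumed. Neither the size nor the direction of the between-group bias can be fixed from the documents, because both depend on how controls are handled and on transfer rates. At 5% transferred with a 10-day true stay, the combinations tabulated run from about 0.18 days against treatment, through zero, to about 0.22 days in its favour. The sample size of 228 reproduces and is not in question on this point. The plan should be changed before analysis.

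**What to change.** - **4.2.1 and 5.5:** define length of stay in both arms as time from hospital admission to hospital discharge, intensive care days included. Measure oxygen time through any transfer. Run outcome data collection to hospital discharge, and reconcile the synopsis, 5.7.2 and 7.3.4 with this.
- **5.2:** apply the intensive care exclusion to status at enrolment in the experimental arm and at an equivalent defined time for controls, for example admission to the general unit.
- **10.4.5:** keep later transfers in the primary analysis whether or not study treatment continued, and report transfers by arm. Align 5.7.1 with this.
- **7.3.5:** add hospital discharge time and oxygen stop time.

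The cost is mainly wording, since the hospital record should hold these times. The statistical cost is variance. If the SD of 3.5 excludes such stays, with share p having d extra days, variance becomes 12.25 + p(1 − p)d²:

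- p = 5%, d = 3: 12.25 + 0.43 = 12.68, about 118 per group for 1.3 days.
- p = 15%, d = 6: 12.25 + 4.59 = 16.84, about 157 per group.

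These inputs are also assumed. The increase is slight if transfers are few and material if they are common, so the stated power should be checked against the resulting SD. The change concerns measurement and analysis only, not clinical management.

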5.6 Total Number of Participants and Sites

Recruitment will end when approximately 114 participants are enrolled. It is expected that approximately 200 participants will be enrolled in order to produce 114 evaluable participants.

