SAE	Serious Adverse Event/Serious Adverse Experience
SOP	Standard Operating Procedure
US	United States

Protocol Summary

Title	Efficacy of combined nebulized hypertonic saline and chest percussion therapy in acute viral bronchiolitis
Short Title	Combined nebulized hypertonic saline and chest percussion in pediatric bronchiolitis
Brief Summary	This study will examine the efficacy of combined nebulized hypertonic saline with chest percussion therapy in patients age 0 to 24 months admitted to the general inpatient pediatrics unit with acute bronchiolitis. 3% nebulized hypertonic saline treatments combined with 3 minutes of chest percussion therapy will be administered every 6 hours of patients selected for the study.
Phase	N/A
Objectives	Primary outcomes measured will be length of hospital stay and time on supplemental oxygen support, both to be measured in hours. The hypothesis will be that combined nebulized hypertonic saline and chest percussion therapy will decrease length of hospital stay and time on supplemental oxygen support. Secondary outcomes measured will be clinical response (respiratory rate, heart rate, pulse oximetry reading), subjective perceptions of caregivers and health care team, and cost-benefit.
Methodology	Cross-sectional quasi-experimental, open, non-randomized clinical study
Endpoint	Primary endpoints include length of hospital stay and time on supplemental oxygen therapy. Secondary endpoints include trend of respiratory rate, heart rate, and pulse oximetry reading following treatments and subjective perceptions of patients' clinical status based on caregiver and health care team.
Study Duration	12 months
Participant Duration	The duration of participation will begin from time of admission to the general inpatient pediatrics unit until time of discharge from the general inpatient pediatrics unit. This duration may vary from patient to patient, on average will last approximately 1-5 days.
Duration of IP administration	The duration of product administration will begin from time of admission to the general inpatient pediatrics unit until time of discontinuation of supplemental oxygen therapy. This duration may vary from patient to patient, on average will last approximately 1-5 days.
Population	Pediatric patients age 0 to 24 months admitted to the general pediatrics unit admitted for acute bronchiolitis requiring supplemental oxygen therapy
Study Sites	NYU Langone Hospital – Long Island, general inpatient pediatrics unit (NP5)

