5.4 Strategies for Recruitment and Retention

Recruitment strategies include identifying patients upon admission to the general inpatient pediatrics unit with the primary diagnosis of acute bronchiolitis that do not meet exclusion criteria for this study. No media services will be required. If a subject requests information regarding opting out of further recruitment for all research, subjects will be directed to contact [contact] or [name].

Informed consent will be obtained at time of admission within private space of patient room and will be conducted in a sensitive manner, allowing consent to be provided in a clearly explained manner. Ample time will be provided for caregivers to decide on consent.

Information collected will be from the patient's medical chart to include age and gender. No other personal information will be required for this study. Only the primary investigator and any future added co-investigators of this study will receive this information. The target sample size for this experimental arm will be 114 patients and it is anticipated that approximately 200 patients will be screened to achieve this number. The source of participants will only be in the general inpatient pediatrics unit.

Upon patients' enrollment into the study, physicians on the patients' care team will be notified via in person or secure chat through the electronic medical record within 1 hour from patients' enrollment into the study and investigators will obtain clearance from these providers to begin the study treatments.

These physicians will also be notified at this time that they will be asked to answer subjective surveys assessing their patients' response to the study treatment. See Appendix 3.

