10.2 Statistical Hypotheses

The statistical hypotheses are as follows:

- Null hypothesis: combined nebulized hypertonic saline nebulization with chest percussion therapy in patients age 0 to 24 months admitted to the general inpatient pediatrics unit with acute bronchiolitis will not have any significant effects on primary outcomes (length of stay and number of days on supplemental oxygen therapy) and secondary outcomes (objective clinical responses included respiratory rate, heart rate, and oxygen saturation and subjective clinical responses from physicians and caregivers).
- Alternative hypotheses: combined nebulized hypertonic saline nebulization with chest percussion therapy in patients age 0 to 24 months admitted to the general inpatient pediatrics unit with acute bronchiolitis will have clinically significant effects on primary outcomes (length of stay and number of days on supplemental oxygen therapy) and secondary outcomes (objective clinical responses included respiratory rate, heart rate, and oxygen saturation and subjective clinical responses from physicians and caregivers).

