10.5 Sample Size

The proposed sample size for this study is 228 subjects ($n=114$ per group). Based on data published by Gajdos, et al., the mean duration of hospitalization for bronchiolitis recorded in the study hospitals during previous years was 6.5 days and standard deviation = 3.5 days. For a type I error of 0.05 and a power of 0.80, for detecting a 20% decrease in duration of hospitalization, a total of 228 subjects would be included (114 subjects in each group).

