10.6 Measures to Minimize Bias

This study is not blinded. All patients who meet the inclusion criteria are eligible to enroll in the study and would be receiving the investigational therapy of nebulized 3% hypertonic saline combined with chest percussion therapy. These participants will be part of the experimental arm of the study. No masking or randomization is required. It is expected that at least 114 subjects in this group will be required to accommodate for a type I error of 0.05 and a power of 0.80. An estimate of approximately 200 participants will be required to be enrolled in this study to account for early withdrawal from the study for any reason.

11 Source Documents and Access to Source Data/Documents

Source data is all information, original records of clinical findings, observations, or other activities in a clinical trial necessary for the reconstruction and evaluation of the trial. Source data are contained in source documents. Examples of these original documents, and data records include: hospital records, clinical and office charts, laboratory notes, memoranda, subjects' diaries or evaluation checklists, pharmacy dispensing records, recorded data from automated instruments, copies or transcriptions certified after verification as being accurate and complete, microfiches, photographic negatives, microfilm or magnetic media, x-rays, subject files, and records kept at the pharmacy, at the laboratories, and at medico-technical departments involved in the clinical trial. It is acceptable to use CRFs as source documents. If this is the case, it should be stated in this section what data will be collected on CRFs and what data will be collected from other sources.

The study case report form (CRF) is the primary data collection instrument for the study. All data requested on the CRF must be recorded. All missing data must be explained. If a space on the CRF is left blank because the

procedure was not done or the question was not asked, write "N/D". If the item is not applicable to the individual case, write "N/A". All entries should be printed legibly in black ink. If any entry error has been made, to correct such an error, draw a single straight line through the incorrect entry and enter the correct data above it. All such changes must be initialed and dated. DO NOT ERASE OR WHITE OUT ERRORS. For clarification of illegible or uncertain entries, print the clarification above the item, then initial and date it.

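### The experimental-arm enrolment target contradicts itself, so the stated 80% power holds only on some readings; the 6.5-day mean stay behind it is unsupported for this unit

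*Combined protocol and SAP*

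**What the plan says.** **Enrolment.** The protocol gives three statements about how many children enter the experimental arm:

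- Section 5.6: "Recruitment will end when approximately 114 participants are enrolled". The next sentence reads: "It is expected that approximately 200 participants will be enrolled in order to produce 114 evaluable participants".
- Section 10.6: "An estimate of approximately 200 participants will be required to be enrolled in this study to account for early withdrawal".
- Section 5.4, after setting the experimental-arm target at 114: "it is anticipated that approximately 200 patients will be screened to achieve this number".

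**Withdrawals.** Section 5.7.2 says that no information from a withdrawn participant, from before or after withdrawal, is used. Section 10.4.5 removes from the study anyone who leaves early, whether because of an adverse event or for another reason.

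**Sizing.** Section 10.5 attributes its inputs to a published multicentre trial of chest physiotherapy: "the mean duration of hospitalization for bronchiolitis recorded in the study hospitals during previous years was 6.5 days and standard deviation = 3.5 days". The target is given as "For a type I error of 0.05 and a power of 0.80, for detecting a 20% decrease in duration of hospitalization", leading to 114 per group and 228 in total. Section 4.1 repeats this with the citation; section 10.4.7.2 repeats it without.

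**Expected stay here.** Under Participant Duration, the Protocol Summary says that the time from admission to the unit until discharge from it "on average will last approximately 1-5 days".

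**The concern.** Screened, enrolled and evaluable are different counts, and the protocol attaches 200 to two of them and 114 to two of them. Site staff cannot both stop at 114 enrolled and enrol about 200. The choice matters because children who withdraw are taken out of the analysis: a loss after enrolment shrinks the analysed treated arm, whereas a screen failure does not. The chart-review controls cannot withdraw, so any such loss falls on the treated arm alone.

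The second issue is the basis of the power claim. A 20% reduction is worth 1.3 days only if the mean stay is 6.5 days. The protocol expects an average stay of about 1-5 days on this unit, a range that does not contain 6.5. No mean or SD of stay for this hospital is given anywhere. A stopping rule and a sizing assumption for a primary endpoint have to be settled before recruitment; they cannot be repaired once it has ended.

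**Working it through.** **Inputs.** From section 10.5: mean 6.5 days, SD 3.5 days, 20% decrease, alpha 0.05, power 0.80, 114 per group. Sidedness is not stated. The null in section 10.2 is non-directional ("will not have any significant effects on primary outcomes"), so I take a two-sided test. From sections 5.6 and 10.6: 200 enrolled for 114 evaluable.

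**Step 1: reproduce the plan's figure.**

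- Difference = 0.20 × 6.5 = 1.3 days.
- n per group = 2 × (1.96 + 0.8416)² × 3.5² / 1.3² = 113.8, rounded up to 114; total 228.

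This matches. A one-sided test would need 90 per group, which supports the two-sided reading. Power at 114 vs 114 is 80.1% by the normal formula and 79.7% by the t distribution. The sample-size arithmetic is sound.

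**Step 2: implied loss.** 1 − 114/200 = 0.43. The protocol never states this rate. Under sections 5.6 and 10.6 it is loss after enrolment; under section 5.4 it is screen failure.

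**Step 3: power under each reading.** Power = Φ[1.3 / (3.5 × √(1/n₁ + 1/114)) − 1.96], where n₁ is the number of evaluable treated children and the 114 controls stay fixed.

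| Reading | n₁ | Power |
|---|---|---|
| About 200 enrolled, 43% lost | 114 | 80.1% |
| About 200 screened, 114 enrolled, none lost | 114 | 80.1% |
| Stop at 114 enrolled, 10% lost (assumed) | 103 | 78.0% |
| Stop at 114 enrolled, 20% lost (assumed) | 91 | 75.2% |
| Stop at 114 enrolled, 30% lost (assumed) | 80 | 72.1% |
| Stop at 114 enrolled, 43% lost (implied) | 65 | 66.6% (t: 66.2%) |

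For the last row, 114 × 0.57 = 65, and 1.3 / (3.5 × √(1/65 + 1/114)) = 1.3 / 0.544 = 2.390; 2.390 − 1.960 = 0.430; Φ(0.430) = 0.666.

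**Step 4: sensitivity to the length-of-stay inputs, at 114 vs 114.** The effect is relative, so power depends on the ratio of SD to mean. The plan's ratio is 3.5/6.5 = 0.54. If that ratio holds here, power is 80.1% at any mean. If it does not, take a mean of 3 days (assumed, the middle of 1-5), so that a 20% cut is 0.6 day:

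| SD (assumed) | Power |
|---|---|
| 1.6 days (ratio 0.54) | about 80% |
| 2.0 days | 62% |
| 2.5 days | 44% |

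The break-even SD for 80% power is 0.54 × mean: about 1.6 days at a mean of 3, and about 2.7 days at a mean of 5.

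**The case against.** The strongest defence is that two of the three readings deliver what section 10.5 promises. If about 200 are enrolled, 114 remain evaluable. If 200 is the screening number, the 43% never enter the study. On either reading power is 80%, and the stop at 114 could be loose drafting. This stands as far as it goes: the documents do not establish which reading is intended. They do, however, contain only one explicit rule for ending recruitment, and it counts enrolled children.

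Several stronger readings are tempting, and the documents do not support them:

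- *The trial will have only 66% power.* This joins the stop rule in one sentence of section 5.6 to a loss rate derived from the next sentence, which plans 200 enrolled. It is the low end of a range. Nor does excluding withdrawals by itself produce 66%: with 200 enrolled, the same exclusion still leaves 114.
- *Both arms shrink to 65, giving about 56%.* Controls come from retrospective chart review and have nothing to withdraw from. Nothing in the protocol reduces them.
- *The true total is 200 + 114 = 314, not 228.* This compares an enrolled count with an analysed one. Enrolling 200 to analyse 114 is compatible with 228 analysed; the number in the Protocol Summary only needs a label.
- *A shorter stay means low power.* The target is a relative reduction. Pairing a 3-day mean with an unchanged SD of 3.5 gives 25% power, but that ratio (1.17) is more than double the plan's, and no site SD is given to justify it.

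The missing citation in section 10.4.7.2 is minor, since sections 4.1 and 10.5 both give the source.

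**Conclusion.** The point holds as an internal contradiction and an unsupported input; the sample-size formula itself is correct. On the plan's own mean, SD and effect, with a two-sided test and 114 controls, power runs from about 66% to 80% depending on which enrolment statement is followed and how many treated children are lost. The 10%, 20% and 30% losses are assumptions; the 43% is implied by 114/200 and not stated.

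The 6.5-day mean conflicts with the protocol's expected stay, so the 80% claim is not supported for this unit. Whether actual power would be lower or higher cannot be determined from the documents, because it turns on a local SD that they do not give. The enrolment contradiction alone warrants correction before recruitment starts.

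**What to change.** 1. **State one rule in sections 5.4, 5.6 and 10.6**, with separate numbers for screened, enrolled and analysed. Preferably: about 200 screened, recruitment ends at 114 enrolled, and all enrolled children are analysed except where consent to use their data is withdrawn. Label the 228 in the Protocol Summary accordingly.
2. **Amend sections 5.7.2 and 10.4.5 to match**, so that stopping study treatment early does not remove a child from the analysis. Without this, the new rule would contradict both sections.
3. **If a stop at 114 enrolled with exclusion of withdrawals is kept instead**, restate power for the expected evaluable number: about 66% at 43% loss, or the matching figure for whatever loss is justified.
4. **Before the first experimental enrolment, take the mean and SD of length of stay from the 12-month control charts.** Restate in sections 10.5 and 10.4.7.2 the power, or the detectable difference, for 114 per group.

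**Cost.** The preferred rule needs no additional patients. It does need the control charts extracted early and basic statistical support at that stage; section 1 says that no biostatistician is yet assigned and defers analysis until one is. The restated power may be less favourable than 80%.
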